3.3 Duration of the study

The planned period for recruiting patients will be 3 months, from the 1st of august to the 31th of October 2018.

The planned dates for the study milestones are provided in the following table

Milestone	Planned Date
Study start date (start of enrolment and data collection)	01/08/2018
Study end date (end of enrolment and data collection)	31/10/2018
Interim analysis	NA
Final report of study results	Q2 2019

The overall duration of the study or the duration of the patient recruitment period may vary depending on the rate at which patients are included or the time it takes to obtain regulatory authorisations.

3.4 Physician recruitment and study initiation

The physician population in this study will include internists and rheumatologists who manage patients suffering from GCA in hospitals or private clinics in France and agree to take part in the study.

A national data base provided by an independent company (CEGEDIM) including approximately 2600 internists and rheumatologists practicing in hospitals or private clinics in Metropolitan France will be used to recruit 150 active physicians for the study.

Physician will be selected by the Sponsor following rules and recommendations on relations between industry and health professionals.

3.5 Patient selection

3.5.1 Patient selection method

Physicians will start patient inclusion only when the study is initiated at their site and when all regulatory authorisations are obtained.

It is expected that 300 patients (prevalent or incident cases) will be recruited in this study. Based on the previous EGB database analysis, there are 2300 incident patients/year in France. Thus, including 300 incident and prevalent patients during the recruitment period, even excluding summer holidays, seems realistic

Each physician will be requested to include consecutively during the inclusion period all the patients meeting the eligibility criteria listed below and accepting to participate in the study.

3.5.1.1 Inclusion criteria

Patients must meet the following criteria to be included in the study:

- At least 50 years old.
- Suffering from GCA as per investigator judgement, newly diagnosed or not.
- Starting or under treatment for GCA.
- Informed verbally and in writing about this study and not objecting to their data being electronically processed or subjected to data quality control.

3.5.1.2 Non-inclusion criteria

Patients fulfilling the following criteria cannot be included in the study:

- Unable to consent
- Participation to a randomised controlled clinical trial

3.5.2 Information and consent

The physician must inform the patient about the study before inclusion and seek her/his non-opposition. A patient information form will be given to each patient by the physician. It will explain the purpose of collecting and processing the data, the nature of data collected, the persons who will receive the data, the patient's right to access and correct the data and also the patient's right to object to transmission of the data (as specified by the CNIL). The original will be kept by the investigator and a copy will be given to the patient.

Patients who are eligible to take part in the study and who verbally agree to their data undergoing automated processing (as defined by CNIL), will be included in the study by the physicians, who will enter the corresponding data in the eCRF. The patient agreement will be only verbal and will NOT include the collection of a non-opposition form.

Patient decision to participate or not in the study will be written in his/her medical file by the physician.

4 STUDY POPULATIONS

Three populations will be defined for the analyses:

- Population of Physicians: all the specialists who have included at least one patient meeting the eligibility criteria for the study
- Enrolled Population: all included patients
- Analysis Population: all included patients meeting the inclusion and non-inclusion criteria

5 STATISTICAL METHODOLOGY

The statistical analysis will be performed by ITEC Services - [name] - FRANCE.

5.1 Descriptive statistics

Each modality of qualitative data will be presented with their number and percentage.

For quantitative data, mean, median, minimum and maximum as well as standard deviation and interquartile range will be described.

For all the variables, number of available and missing observations will be specified. If necessary, 95 % CI will also be presented.

Data will be presented using an appropriate number of decimal places (i.e. the number of decimal places used does not imply undue precision):

- Raw data : same number of decimal as collected,
- Derived data: The appropriate number of decimal places will be determined by general practice, mathematical rationale or scientific rationale (e.g. age should be presented in whole numbers),
- Mean, median and standard deviation : reported to one decimal place greater than the raw/derived data that they summarise,
- Minimum and maximum : same precision as the raw data,
- Percentage : one decimal place,
- P-values : four decimal places (e.g.: $p=0.0037$), after rounding. P-values which are less than 0.0001 will be presented as '<0.0001'.

5.2 Management of missing values

5.2.1 Missing data

Missing data will not be replaced.

5.2.2 Missing or incomplete dates

For all dates

- if only the day part is missing, it will be replaced by 15 (only when date is in format DD/MM/YYYY)
- if only the month part is missing and it is a former date (for example the date of diagnosis), it will be replaced by June
- if the day and month parts are missing and it is a former date (for example the date of diagnosis), day will be replaced by 1 and month will be replaced by July

- if the year part is missing or the complete date is missing, no replacement will be performed and calculation will be considered as missing

5.2.3 Outliers

Any outlier identified prior to database lock which is impossible/implausible will be excluded from the analysis. A search of outliers should be performed before the database lock and actions with the sponsor should be defined (during data review meeting).

5.3 Disposition of patients

Key information of the study (including date of inclusion of the first patient and the last patient, enrollment duration ([APPENDIX](#)), number of participating physicians) will be presented.

A flowchart and an associated table will be provided to present overall and by type of physicians who follows the patient

- The number of patients enrolled
- The number of patients not included and their reason for non-inclusion

5.4 Analyses of primary objectives

To describe medical practices in patients with GCA, the following endpoints will be described on the analysis population:

- Patient journey
 - Proportion of each medical speciality of the physician who has referred the patient (General practitioner/ Ophthalmologist / Neurologist/ Emergency/ Internist/ Rheumatologist/Other)
A listing of Other will be presented.
 - Proportion of each medical speciality of physicians who follows the patient for his/her GCA (Internist/ Rheumatologist/Other)
A listing of Other will be presented.
 - Time between the first medical events related to GCA and diagnosis (months) (type of diagnosis) described as quantitative variable and as qualitative variable. (Early diagnosis (if < 1month) / Diagnosis in the standard time (if between 1 month and 3 months) / Late diagnosis (if > 3 months)) ([APPENDIX](#))
 - Proportion of patients considered with late diagnosis by the physician who referred the patient (Yes/No)
 - Proportion of patient who encountered each medical speciality since the first events related to GCA (Horton).
 - Number of type of medical specialities encountered by the patient since the first events related to GCA (Horton). If a patient encountered a medical speciality more than one time, this speciality will be counted only once.

The first 2 endpoints will be described overall and by time between first medical events and diagnosis (Early diagnosis/ diagnosis in the standard time/ late diagnosis)

The 1st,3rd and 4th endpoints will be described overall and by type of physicians who follows the patient.

- Diagnostic elements used for GCA diagnosis
 - Proportion of each diagnostic element
 - Signs/symptoms (Yes/No/ intermediate)
 - Erythrocyte Sedimentation Rate (ESR) done (Yes/ No)

- If yes, contributing to diagnosis (Yes/ No/ intermediate)
- C-Reactive protein (CRP) done (Yes/ No)
 - If yes, contributing to diagnosis (Yes/ No/ intermediate)
- Biopsy of the temporal artery (TAB) done (Yes/ No)
 - If yes, contributing to diagnosis (Yes/ No/ intermediate)
- High resolution color Doppler ultrasound of the temporal arteries done (Yes/ No)
 - If yes, contributing to diagnosis (Yes/ No/ intermediate)
- MRI scanner of the temporal arteries done (Yes/ No)
 - If yes, contributing to diagnosis (Yes/ No/ intermediate)
- 18FDG PET positron emission tomography done (Yes/ No)
 - If yes, contributing to diagnosis (Yes/ No/ intermediate)
- Aortic angiography by CT (angio-CT) done (Yes/ No)
 - If yes, contributing to diagnosis (Yes/ No/ intermediate)
- Magnetic resonance angiography done (Yes/ No)
 - If yes, contributing to diagnosis (Yes/ No/ intermediate)
- Other (Yes/No/ intermediate)

A listing of other methods will be presented.

Only diagnostic methods done in the previous month of date of diagnosis, the current month of the day of diagnosis and the month following the date of diagnosis will be considered. The diagnostic methods will be described overall, by time between first medical events related to GCA and diagnosis (qualitative variable), and by type of physicians who follows the patient.

- Previous and ongoing specific GCA treatments since diagnosis other than GCs
 - Number of patients who has taken at least one immunosuppressant since diagnosis and stopped before inclusion and the frequency of each type (Methotrexate, Cyclophosphamide, Cyclosporine, Azathioprine, Mycophenolate Mofetil, Leflunomide, Other) and duration of each treatment taken (months), ([APPENDIX](#))
 - Number of patients with at least one immunosuppressant ongoing at inclusion and frequency of each type (Methotrexate, Cyclophosphamide, Cyclosporine, Azathioprine, Mycophenolate Mofetil, Leflunomide, Other), dose at the initiation (mg), maximal dose (mg), current dose (mg) and duration of each treatment taken (months).([APPENDIX](#))
 - Number of patients who has taken at least one targeted biological therapy since diagnosis and stopped before inclusion and the frequency of each type (Adalimumab, Etanercept, Abatacept, Tocilizumab, Infliximab, Other) dose at the initiation (mg) and duration of each treatment taken (months) ([APPENDIX](#))
 - Number of patients with at least one targeted biological therapy ongoing at inclusion and the frequency of each type (Adalimumab, Etanercept, Abatacept, Tocilizumab, Infliximab, Other) dose at the initiation current dose and duration of each treatment taken (months) ([APPENDIX](#))
 - Number of patients who has taken at least one other long-term treatment for the medical care of GCA since diagnosis and stopped before inclusion and the frequency of each type (Baricitinib, Dapsone, Hydroxychloroquine, Tofacitinib, Other), dose at the initiation, maximal dose and duration of each treatment taken (months) ([APPENDIX](#))
 - Number of patients with at least one other long-term treatment for the medical care of GCA ongoing at inclusion and the frequency of each type (Baricitinib, Dapsone, Hydroxychloroquine, Tofacitinib, Other) dose at the initiation, maximal dose, current dose and duration of each treatment taken (months) ([APPENDIX](#))

A listing of specifications of other treatments (immunosuppressants, targeted biological therapy, and other long-term treatments) will be presented.

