The index date was defined as the date of first occurrence of GCA code and cases were considered being incident if the GCA code first occurred after a minimal follow-up of 2 years. A treatment sequence was defined as the start of a new drug or the resumption of the same drug after a stop of drug dispensing ≥ 3 months. Annual incidence rates were calculated for the period 2009 to 2015 by using the people recorded in the EGB database as denominator.

Briefly, the results were the following: among the 752,717 patients recorded in the EGB database, 241 people fulfilled inclusion criteria with a mean follow-up of 3.7 (± 2.6) years. Annual incidence was ranging between 7 and 10/100,000 people ≥ 50 years-old that is 2300 patients/year. Demographic analyses showed that 72% of the patients were females and that mean age was 77.5 (± 8.9) years. 74.3% of the patients had at least one proxy (i.e ICD-10 code or a treatment) for hypertension, 39.4% for depression/insomnia and 33.6% for osteoporosis. After index date, temporal artery biopsy (TAB) was performed in 43.2%, high-resolution color Doppler ultrasound in 35.3% and 18FDG-positron emission tomography (PET) in 11.6%.

Regarding treatments, 84.3% of the patients used only GCs while 16.7% also received 1 to 3 adjunctive medications, mainly MTX. Mean 1st GCs sequence duration was 17.2 months (± 16.5) in 96.6% of the patients.

EGB database strengths included comprehensive patient demography, epidemiology, diagnostic methods and treatment sequences. In contrast, limited data were available for comorbidities (as only proxies were described), clinical presentations (cranial, polymyalgia rheumatica [PMR], extracranial), clinical forms (relapsing, GCs-dependant), doses of GCs used, cumulative GCs doses and GCs associated toxicities. In addition, patient journey was poorly described given that patients may be first seen by a variety of physicians according to their first signs and symptoms (e.g. ophthalmologist for blurred vision, neurologist for headache, etc.), data which was not available in the EGB database analysis.

The proportions of use of TAB, Ultrasound or PET have also to be confirmed as they thought to be unusually performed in the EGB analysis.

We propose to conduct an observational study aiming to describe GCA management and patient characteristics in France.

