5.3.1 Case report form

No information related to patient identity (initials, full date of birth, etc) will be entered in the eCRF.

The following information will be recorded in the eCRF using the data available in the medical file or collected during the visit (as part of the routine patient management):

- » Date of the inclusion visit (the only study visit) and type of visit (outpatient visit, day hospital, in-patient hospitalisation).
- » Patient eligibility criteria.
- » Demographic data:
 - Year of birth, gender,
 - Smoking status (smoker, never smoker),
- » Clinical data:
 - Height, weight (at diagnosis, at the inclusion visit)
 - Medical history:
 - significant past and current comorbidities (e.g. diabetes, high blood pressure, dyslipidaemia, osteoporosis, neuropsychiatric disorders,

depression, insomnia, serious infection disease, parasitic diseases, cancer, stroke, coronary artery disease, ischemic cardiopathy, peripheral artery diseases, adrenal insufficiency, cataract, glaucoma, gastro-intestinal ulcer, digestive perforation, other significant history),

- start and stop date (month, year) of comorbidities
- Comorbidities related to GCs for GCA patients (i.e. which appeared or worsened during GCs treatment according to the investigator judgement).

» GCA patient journey:

- Incident or prevalent patient:
 - Newly diagnosed (i.e. incident) patient will be defined as patient with GCA diagnosis within the last 6 weeks before visit
 - Not newly diagnosed (i.e. prevalent) patients will be defined as patient with GCA diagnosis more than 6 weeks before visit
- Date of initial diagnosis
- Date of GCA signs/symptoms (month and year)
- Physician(s) who referred the patient (General Practitioner, Ophthalmologists, Neurologist, Emergency, Internist, Rheumatologist, Other).

» GCA characteristics:

- Initial presentation at diagnosis and inclusion visit:
 - Cranial (localized headache, scalp tenderness, temporal artery tenderness or decreased pulsation, ischemia-related vision impairment / loss, mouth or jaw pain upon mastication, stroke or transient ischaemic attack (TIA), other)
 - PMR (morning stiffness and/or pain in the shoulder and/or pelvic girdles, inflammatory arthromyalgia, peripheral arthritis, other)
 - Extracranial (large-vessel GCA i.e. thoracic or abdominal aortic aneurysm, myocardial infarction, dilatation, limb claudication, subclavian stenosis, other)
 - ESR/CRP
 - General signs: fever, weight loss (%), health status modification

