7 STATISTICAL METHODS

7.1 Rationale for the number of patients and physicians

7.1.1 *Number of patients required*

Not applicable in a descriptive observational study

7.1.2 *Number of physicians*

Not applicable

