7.2 Statistical analyses

The analysis will be performed by ITEC Services in accordance with this section and with the Statistical Analysis Plan (SAP) that supplements it.

7.2.1 *General statistical methods*

The statistical analysis will be performed using SAS® software, version 9.3 or upper.

A SAP describing the planned statistical analysis in detail with Tables, Figures and Listings (TFLs) templates will be developed as a separate document. This SAP will be finalised and validated before each database freeze by CPF.

The descriptive summary statistics will be:

- » for quantitative parameters: mean, standard deviation, median, first and third quartiles, minimum and maximum, filled and missing data;
- » for qualitative parameters: frequency, percentage per modality, filled and missing data

As this is a descriptive study, no statistical testing will be performed. However, 2 sided 95% confidence intervals will be calculated for every relevant proportion / mean.

7.2.2 *Study populations*

Three populations will be defined for the analyses:

- » Population of Physicians: all the specialists who have included at least one patient meeting the eligibility criteria for the study
- » Total Population: all included patients
- » Analysis Population: all included patients meeting the inclusion and non-inclusion criteria

The number of potential exclusions from the patient population used for analysis and the reasons for these exclusions will be described. The patient disposition will be described.

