7.2.3 Analysis of the physician and patient populations

The analyses of the primary and secondary objectives will be performed on the Analysis Population.

7.2.3.1 Analyses of primary objectives:

To describe medical practices in patients with GCA, the following endpoints will be described on the analysis population:

Patient journey

- » Proportions of each physician who referred the patient
- » Proportions of each physician who follows the patient for his/her GCA (internist/rheumatologist)
- » Time between signs/symptoms and diagnosis: described as quantitative variable and as qualitative variable. (early diagnosis / diagnosis in the standard time / late diagnosis)

The 3 endpoints will be described overall and by subgroups: the first 2 endpoints will be described by time between signs/symptoms and diagnosis (qualitative variable) and the 1st and 3rd endpoints will be described by type of physicians who follows the patient.

Diagnostic mean

- » Proportions of each diagnostic method used

The diagnostic mean will be described overall, by time between signs/symptoms and diagnosis (qualitative variable), and by type of physicians who follows the patient.

Previous and on-going specific GCA treatments since diagnosis

- » Previous and on-going specific GCA treatments since diagnosis

Treatments will be coded using the WHO Drug medicine dictionary (ATC codes). They will be described overall and by type of physician who follows the patient.

7.2.3.2 *Analyses of secondary objectives*

The analysis of the secondary objectives will be performed on the analysis population.

Description of comorbidities related to GCs and associated treatments

- » Current and past comorbidities of GCA patients (comorbidities related to GCs) will be coded using the medical dictionary MedDRA®. They will be described overall and by type of physicians who follows the patient.
- » Treatments in patients with comorbidities related to GCs will be coded using the WHO Drug medicine dictionary (ATC codes). They will be described overall and by type of physician who follows the patient.

Description of GCA characteristics

- » Time between diagnosis and inclusion will be described as quantitative variable and as qualitative variable (patient newly diagnosed or not: incident or prevalent case)
- » Proportion of incident patients: patients with a diagnosis of GCA \leq 6 weeks from inclusion
- » Proportion of prevalent patients: patients with a diagnosis of GCA $>$ 6 weeks from inclusion.

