The following endpoints will be described overall and by type of patient (prevalent/incident), by time between signs/symptoms and diagnosis (qualitative variable), and by type of physicians who follows the patient:

- » GCA duration
- » Initial presentation: proportions of patients with cranial GCA, PMR, extracranial GCA, ESR/CRP, general signs
- » Clinical form
 - Proportion of patients with relapse and number of relapse,
 - Proportion of patients with recurrence and number of recurrences,
 - Dose of GCs-dependence
 - Proportion of patients with GCA complications.

Analysis of potential factors associated to relapse will be performed using logistic regression. The associated factors will be defined in the SAP.

- » GCA activity
 - Proportions of each clinical signs/symptoms of GCA activity

- Scores of the patient and physician global arteritis activity VAS (quantitative variable)

The concordance between the scores of the patient and physician global arteritis activity VAS will be evaluated using the kappa coefficient.

The potential factors associated with the increase of the global arteritis activity will be studied.

Description of the health status of GCA patients

» SF-36 questionnaire

The SF-36 is a self-report, 36 item survey measuring health-related quality-of-life. The SF-36 consists of eight scaled scores. A score ranging from 0 (indicating the worse health status) to 100 (indicating the best health status) is assigned for each domain. Scores and missing data of the SF-36 were handled according to the user's manual. The score for each item of SF-36 will be presented (in quantitative) as well as the total score for each domain.

» EQ5D-3L questionnaire

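### The primary non-glucocorticoid treatment tables (SAP Tables 6–11) pool newly diagnosed and established patients, so the stopped, ongoing and duration figures depend partly on an uncontrolled recruitment mix

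*SAP*

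**What the plan says.** **Who enters.** Both newly diagnosed and established patients are eligible (Protocol 4.2.1). SAP 3.5.1 states: "It is expected that 300 patients (prevalent or incident cases) will be recruited in this study". Inclusion is consecutive, and the only cap is 10 patients per hospital department (Protocol 4.1). There is no quota or target mix by patient type. On the number of patients required, Protocol 7.1.1 says "Not applicable in a descriptive observational study".

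**The flag.** Protocol 5.3.1 classes every patient, under the patient journey: "Newly diagnosed (i.e. incident) patient will be defined as patient with GCA diagnosis within the last 6 weeks before visit". Anyone diagnosed earlier is prevalent.

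**Primary treatment endpoints.** SAP 5.4 counts "Number of patients who has taken at least one immunosuppressant since diagnosis and stopped before inclusion", does the same for targeted biologics and for other long-term drugs, and gives matching counts for drugs ongoing at inclusion, with durations. Protocol 7.2.3.1 says of these treatments: "They will be described overall and by type of physician who follows the patient". SAP 5.4 names no subgroup for them, and the shells of Tables 6–11 have a single total column. Listing 3 carries the newly/not newly diagnosed flag, but only for treatments recorded as other.

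**Where the flag is used.** For the secondary GCA characteristics, Protocol 7.2.3.2 says "The following endpoints will be described overall and by type of patient (prevalent/incident") and also by diagnostic delay and following physician; SAP 5.5.2 repeats this. Table 14 reports the incident/prevalent mix, and patient type is a candidate factor in both logistic models.

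**Precision.** Protocol 7.2.1 promises that "2 sided 95% confidence intervals will be calculated for every relevant proportion / mean". SAP 5.1 gives intervals only if necessary, and the shells of Tables 6–11 have no interval row.

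**The concern.** A proportion of patients who started a drug after diagnosis and stopped it before the visit needs a population with time to do both. Patients diagnosed within the last 6 weeks scarcely have that time, yet they count in the denominator. Durations have a similar problem: an incident user contributes a short, truncated duration, while a prevalent user's duration is open-ended. Two samples drawn from identical practice but with different incident shares would therefore give different primary treatment figures. Reporting the mix in Table 14 does not let a reader recover the two groups' own rates for ongoing drugs, or their durations. What is at stake is whether one of the three parts of the primary objective can be interpreted.

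**Working it through.** The plan has no precision or sample-size figure to reproduce. The check has five steps.

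**1. Limits for an incident patient.** SAP section 8, derived variable (4), computes duration in calendar months as end (or inclusion) month − start month + 1. Take a drug started at diagnosis on 31 July and a visit 42 days later, on 11 September: 9 − 7 + 1 = 3 months. Forty-two days can cross at most two month boundaries, so 3 is the ceiling for any drug started since diagnosis. Duration rows are computed among users of each drug only, so incident users shorten them and incident non-users have no effect.

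**2. Incident share, f.** The documents do not give it. Two rough routes:

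- *Caseload.* Inputs: 2300 incident cases per year (Protocol 3.5.1), 150 active physicians out of about 2600 (Protocol 3.4.1), and recruitment of 3 months (SAP 3.3) or 5 months (Protocol 3.3). Six weeks is 42/30.4375 = 1.38 months.
  - 2300 × 150/2600 = 132.7 per year
  - 132.7 × (3 + 1.38)/12 = 48.4, and 48.4/300 = 16.1%
  - 132.7 × (5 + 1.38)/12 = 70.5, and 70.5/300 = 23.5%
  - This assumes that active physicians have an average caseload and include every such patient.
- *Steady state.* The earlier database study's mean first glucocorticoid sequence is 17.2 months (Protocol 1). 1.38/17.2 = 8.0%, or 24 of 300.

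A higher share is possible: 2300 × 3/12 = 575 and 2300 × 5/12 = 958 new diagnoses nationally during recruitment.

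**3. Effect on a pooled proportion.** Pooled = f × p(incident) + (1 − f) × p(prevalent). As an illustration, take p(prevalent) = 16.7%, the earlier study's share with an adjunctive drug, and p(incident) = 0% or 5%.

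| f | p(incident) = 0% | p(incident) = 5% | Fall from 16.7%, points |
|---|---|---|---|
| 8% | 15.4% | 15.8% | 0.9–1.3 |
| 16% | 14.0% | 14.8% | 1.9–2.7 |
| 24% | 12.7% | 13.9% | 2.8–4.0 |

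The 95% half-width at 16.7% and n = 300 is 1.96 × √(0.167 × 0.833/300) = 4.2 points.

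**4. Which other primary rows share the problem.** In Table 2, the specialities encountered since the first events have no stated end point and accumulate with time. Referring specialty and time to diagnosis are fixed at diagnosis. Table 5 counts tests done in the month before, of or after diagnosis for every patient (SAP 5.4), so its window does not depend on disease duration.

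**5. Precision after a split.** Half-width at 50% = 1.96 × √(0.25/n).

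| n | Half-width, points |
|---|---|
| 300 (overall) | 5.7 |
| 240 (prevalent, if 60 are incident) | 6.3 |
| 70 | 11.7 |
| 50 | 13.9 |
| 24 | 20.0 |

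**The case against.** The strongest reply is that consecutive inclusion makes the pooled figure a legitimate cross-section of treated patients being seen, and that much is already handled. Table 14 gives the mix and the time since diagnosis. SAP 5.5.2 splits glucocorticoid exposure, relapses and treatment around relapse by patient type, and glucocorticoids are the mainstay of treatment. If almost no incident patient has stopped a drug, the prevalent rate for Tables 6, 8 and 10 is roughly the reported count divided by Table 14's prevalent total.

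Much of this stands. The pooled figure is a valid description of the sample. But the shortcut is only approximate, because table percentages use filled data as denominator, and it does not work for ongoing drugs or for durations. The glucocorticoid split does not cover the drugs that SAP 5.4 makes primary.

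Two objections to the size also stand. The 16.7% is any adjunctive drug ever used, and no row of Tables 6–11 reports that; it also comes from a pair of percentages adding to 84.3 + 16.7 = 101.0. And at the estimated shares the shift is no larger than the sampling half-width.

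Finally, a split does not make the prevalent group homogeneous: it runs from just over 6 weeks to many years since diagnosis.

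**Conclusion.** The point holds for Tables 6–11 and for the Table 2 rows on specialities encountered. The dependence on mix is structural for stopped treatments and for durations. Its size rests on an incident share that the documents do not give: about 2 to 4 points at 16–24% under the illustrative rates, and about 1 point at 8%. It is an inexpensive improvement to interpretability and does not invalidate the analysis.

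A reader might infer more than the documents support:

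- *That the diagnostic and journey tables are equally affected.* The fixed window of Table 5, and the fact that referral and delay are settled at diagnosis, mean that those figures move with the mix only if the two groups truly differ.
- *That current diagnostic practice should be read from incident patients.* Their month after diagnosis may be unfinished at the visit, so tests could be undercounted.
- *That confirming test use is the primary objective.* The remark "The proportions of use of TAB, Ultrasound or PET have also to be confirmed" is in the Protocol's introduction; the objective in section 2.1 is to describe.
- *That a split would restore comparability with the earlier database study.* That study selected patients by claims codes and dispensing; this one takes treated patients by investigator judgement.
- *That the pooled figure could halve.* At f = 50% and p(incident) = 0% it would be 0.5 × 16.7 = 8.35%, but neither estimate of the share comes near 50%.
- *That the comorbidity and health-status tables (12 and 28–31) need the same split.* The start-and-stop argument does not extend to them.

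**What to change.** In SAP 5.4:

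- Present Tables 6–11, and the Table 2 rows on specialities encountered since the first events, by type of patient (incident/prevalent) as well as overall, using the existing flag and adding 95% confidence intervals.
- State that stopped treatments and treatment durations are to be read from the prevalent column.
- Optionally repeat Table 5 by type of patient as a descriptive check, keeping the overall column as the main estimate because the month after diagnosis may be incomplete in incident patients.

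This needs SAP wording and extra table columns, and no new data. The drawback is an imprecise incident column, which the intervals will make plain. The prevalent column loses little precision.
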